## VI. Background Introduction & Significance

**Research Purpose:** Our study aims to investigate the diagnostic utility and safety of the Magnetically Assisted Capsule Endoscopy (MACE) system compared to traditional esophagogastroduodenoscopy (EGD) in the surveillance of esophageal varices in patients with biliary atresia (BA). Additionally, we seek to determine whether MACE generates fewer aerosols than EGD during the examination, thereby potentially reducing the risk of SARS-CoV-2 transmission.

**General Background Information:** Biliary atresia (BA) is one of the leading causes of chronic liver failure, liver cirrhosis, esophageal varices, and the need for liver transplantation during childhood worldwide (1-4). Statistically, approximately 50% of patients with BA develop portal hypertension, and 26.5% are at risk of gastrointestinal variceal bleeding (5-7). Esophageal variceal bleeding often results in significant complications and risks. In adult patients with chronic hepatitis, clinical indicators such as APRI, FIB-4, Extended Baveno, or Baveno VI are commonly used to help predict the presence of significant esophageal varices (8, 9). However, previous studies in BA patients have shown that these clinical indicators are not accurate in predicting the risk of esophageal varices in this population. Therefore, in clinical practice, physicians still rely on invasive esophagogastroduodenoscopy (EGD) to diagnose and assess the severity of esophageal varices. Based on the severity of the esophageal varices, physicians adjust medication dosages to reduce the risk of unexpected variceal bleeding and its associated complications.

Since the outbreak of SARS-CoV-2 in Wuhan, China in 2019, COVID-19 has continued to spread widely across the globe and has been confirmed as a direct contact and droplet infection disease. As of

Approval Number: 202210059DIPA

June 2022, COVID-19 has resulted in nearly 541 million infections and over 6.3 million deaths worldwide. In Taiwan, it has caused 3.44 million infections and more than 6,000 deaths. Consequently, the pandemic has placed enormous pressure and strain on global healthcare systems. During the outbreak in Europe in 2021, it was reported that over 20% of healthcare workers in northern Italy were infected, severely disrupting normal medical operations and preventing patients with chronic illnesses from receiving necessary medical care (10).

Since conventional esophagogastroduodenoscopy (EGD) has been confirmed as a respiratory droplet-generating medical procedure (11), healthcare workers performing EGD during the COVID-19 pandemic are at risk of being exposed to patient infections during the examination (12). In response, international medical societies have developed guidelines recommending appropriate personal protective equipment (PPE) for endoscopists, pre-procedural COVID-19 screening, requirements for the endoscopic environment, and prioritization criteria for urgent versus elective endoscopic procedures during the pandemic (13-20). Elective and surveillance EGDs were often recommended to be postponed or deferred. During the pandemic in Taiwan, limitations in hospital bed availability, healthcare workforce shortages, and patient anxiety also led to the postponement or deferral of many routine endoscopic examinations. However, in patients with biliary atresia (BA), regular endoscopic surveillance and appropriate medical adjustment have been validated as crucial strategies to prevent unexpected esophageal variceal bleeding (21). Delaying routine endoscopic surveillance and medical interventions in BA patients may increase the risk of unexpected variceal bleeding and life-threatening events. In addition, during periods of severe COVID-19 outbreaks, patients often hesitated or declined routine medical examinations, further leading to disease progression and deterioration.

Therefore, how to balance the medical needs of patients with biliary atresia (BA) and ensure that they receive necessary endoscopic examinations during the pandemic, while protecting both patients and endoscopy personnel from COVID-19 infection to maintain the proper functioning of healthcare systems, has become an important medical issue. Magnetic-assisted capsule endoscopy (MACE) is a novel design that utilizes a disposable, externally magnetically controlled capsule connected by a tether to guide its movement through the gastrointestinal tract (22, 23). Previous studies conducted in Taiwan have already demonstrated the safety and diagnostic accuracy of MACE for upper gastrointestinal examinations (22, 23), while also avoiding the risks associated with anesthesia. Although MACE requires swallowing a tether, its invasiveness remains significantly lower than that of conventional endoscopy. Preliminary studies have shown favorable safety and patient acceptance (22, 23). During the examination, the patient swallows the capsule similarly to taking a pill, and can keep their lips closed and wear a mask throughout the procedure.

Approval Number: 202210059DIPA

This study aims to evaluate whether MACE can achieve diagnostic performance comparable to traditional EGD in detecting esophageal varices in BA patients, while reducing aerosol generation during the procedure, thereby protecting both patients and endoscopy personnel from the risk of SARS-CoV-2 infection.

## VIII.Experiment Designs & Methods

### (I.) Patient eligibility

#### A.Inclusion criteria:

- (A.) Biliary atresia patients > 6 years old
- (B.) Vital signs are stable
- (C.) Without acute gastrointestinal bleeding

#### B.Exclusion Criteria:

- (A.) Patients with metal implants, metal stent, artificial joints, bone plates, and bone screw
- (B.) Patients with electronic devices, such as pacemakers, cochlear implants, or other

Approval Number: 202210059DIPA

implanted electronic medical devices

- (C.) Throat or esophageal obstruction leading to dysphagia patients
- (D.) Consciousness disturbance patients unable to swallow
- (E.) Patients with acute upper gastrointestinal bleeding
- (F.) Patients with platelet lower than 40K or PT INR > 1.5

(II.) Design of experiments:

A. Study Design: Prospective open-label trial.

B. Trial Procedure:

(A.) Endoscopic Examination

In this study, 25 patients aged 6 years or older with biliary atresia undergoing Magnetic-Assisted Capsule Endoscopy (MACE) for esophageal varices survey will be enrolled as the "study group," while another 25 patients aged 6 years or older with biliary atresia undergoing conventional esophagogastroduodenoscopy (EGD) for esophageal varices survey will be enrolled as the "control group." Both groups will prospectively enter the study after providing informed consent and signing the consent form. All patients will fast appropriately according to endoscopic examination guidelines before the procedure. Patients undergoing conventional EGD may choose to receive conscious sedation based on clinical needs. Patients undergoing MACE will be advised to keep their lips closed and wear a surgical mask during the examination. We will compare clinical parameters between the two groups, including examination completion rate, pain perception during the procedure, safety, and willingness to undergo the same examination again in the future.

(B.) Droplet Particle Measurement

During examinations in both the "study group" and the "control group," we will use the MET ONE airborne particle counter [DR-528 Handheld Particle Counter (Met One Instruments, Inc., Grants Pass, OR)], placed on a platform at the same horizontal level as the patient lying flat, to simultaneously measure the number of droplet particles generated during the procedure. We will then compare the differences in droplet particle counts between the two groups. The primary endpoint of this study is to analyze the

Approval Number: 202210059DIPA

difference in the number of droplet particles generated during the examinations between the "study group" and the "control group." The secondary endpoints are to analyze the examination completion rate, pain perception during the procedure, safety, and willingness to undergo the same examination again between the two groups.

(C.) Project Period: 11/01/2022-12/31/2026 (MM/DD/YYYY)

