## IX. Required Medications or Medical Equipment and Quantities

- (I.) Magnetically Assisted Capsule Endoscopy (InsightEyes EGD): 50 sets
- (II.) Aries E500i Image Processor (including power cable) / Aries E500i (Model: FG-270-0008, Quantity: 1)
- (III.) InsightEyes Image Connector / InsightEyes EGD Dongle (Model: DG-001T, Quantity: 1): A connector that links the InsightEyes EGD to the image processor.
- (IV.) InsightEyes MFN Magnetic Controller / InsightEyes MFN (Model: FG-270-0001, Quantity: 1): A magnetic device used to manipulate and adjust the positioning angle of the InsightEyes EGD.

Stationary equipment: ② Aries E500i Image Processor ① Medical-grade monitor (not included in this product) ③ InsightEyes Image Connector  
 Controller: ⑤ InsightEyes MFN Magnetic Controller  
 Single-use medical devices: ④ InsightEyes EGD

The above equipment has been approved by the Taiwan Food and Drug Administration (TFDA) under Medical Device Permit No. 006509.

(V.) MET ONE airborne particle counter [DR-528 Handheld Particle Counter (Met One Instruments, Inc., Grants Pass, OR)]

**X. Format of medical record forms:** Study personnel will use separate case report forms (CRFs).

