**XI. Methods for Data Collection, Processing, Evaluation, and Statistical Analysis**

**Approval Number: 202210059DIPA**

(I.) Collect and record the enrolled patients' basic information (including sex, age, height, weight, past medical history, and medication history), vital signs, pain index, blood test results within the past three months, and transient elastography values.

(II.) Document the examination results of both the Magnetically Assisted Capsule Endoscopy (MACE) and conventional esophagogastroduodenoscopy (EGD), including the presence of esophageal varices and bleeding sites.

(III.) Record the patients' acceptance of the examination and any adverse effects.

(IV.) Record the particle count measurements obtained using the MET ONE Airborne Particle Counter [DR-528 Handheld Particle Counter (Met One Instruments, Inc., Grants Pass, OR)].

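### Does the comparison fail because Section XI does not list sedation given to EGD patients or mask and lip-closure adherence in MACE patients?

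*Combined protocol and SAP*

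**What the plan says.** Section VIII (II.) B.(A.) describes the two examinations. On the EGD side: "Patients undergoing conventional EGD may choose to receive conscious sedation based on clinical needs". On the capsule side: "Patients undergoing MACE will be advised to keep their lips closed and wear a surgical mask during the examination". No sedation option is mentioned for MACE, and none is forbidden.

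The background (Section VI) treats these features as part of what each examination is. MACE is presented as "while also avoiding the risks associated with anesthesia"; it is said that "its invasiveness remains significantly lower than that of conventional endoscopy"; and the patient "can keep their lips closed and wear a mask throughout the procedure". The abstract (Section V) likewise gives mouth closure and the mask as the reason to expect less aerosol.

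The primary endpoint is the between-group difference in particle counts. The secondary endpoints are completion together with "pain perception during the procedure, safety, and willingness to undergo the same examination again between the two groups".

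Section XI lists what is collected: basic information including medication history, then "vital signs, pain index, blood test results within the past three months, and transient elastography values", followed by examination findings, acceptance, adverse effects and particle counts. Section X says separate case report forms will be used; they are not reproduced. Section XII plans two-group tests at the 0.05 level and, for the sample size, takes it that the study group is masked, with filtration of 87-90%.

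**The concern.** Each group has a feature that could move an endpoint, and neither feature is named among the data to be collected. If an unknown share of EGD patients is sedated, the EGD pain score is an average over two different experiences. Sedation could then make EGD look gentler than an unsedated examination would be, or offset a real advantage of the capsule over unsedated EGD. For the primary endpoint, the mask is advised in Section VIII but assumed in Section XII. In patients who may be about six years old, adherence could well be incomplete, and a particle count alone does not show whether the mask stayed on.

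At stake would be the meaning of the secondary results on pain and willingness, and the link between the particle result and the mask assumption. Sedation can probably be recovered from the clinical record later; mask and lip behaviour may not be.

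**Working it through.** **1. The plan's own figure.** The only related number is the sample size of 50. With a 95% interval and a 5% margin, n = 1.96² × p(1 − p) / 0.05². This gives 174 at p = 0.87 and 139 at p = 0.90, so 50 does not follow from the stated inputs. That is a separate matter. It does mean that adherence data would not validate the sample size.

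**2. Sedation: what does the t-test reject?** From the protocol: 25 per group, alpha 0.05 (taken as two-sided), Student t-test. Assumed, because the documents give no values: normal pain scores with SD 2.5; 6, 12 or 19 of 25 EGD patients sedated; sedation lowering pain by 1, 2 or 3 points. Each cell has 40,000 simulated trials.

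If sedation lowers pain by s in k of 25 patients, and MACE is d points less painful than unsedated EGD, the true difference between practices (MACE minus all EGD) is s × k/25 − d.

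*(a) MACE equal to unsedated EGD (d = 0)*

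| s | true difference, k = 6 / 12 / 19 | t-test rejects |
|---|---|---|
| 1 | 0.24 / 0.48 / 0.76 | 6 / 10 / 18% |
| 2 | 0.48 / 0.96 / 1.52 | 9 / 24 / 54% |
| 3 | 0.72 / 1.44 / 2.28 | 14 / 44 / 86% |

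*(b) MACE 2 points better than unsedated EGD (d = 2)*

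| s | true difference, k = 6 / 12 / 19 | significant for MACE |
|---|---|---|
| 0 | −2 | 79% |
| 1 | −1.76 / −1.52 / −1.24 | 67 / 55 / 40% |
| 2 | −1.52 / −1.04 / −0.48 | 54 / 27 / 9% |
| 3 | −1.28 / −0.56 / +0.28 | 38 / 9 / 1% |

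In (a) the rejection rate rises with the true difference between practices. In (b) the chance of success falls as that difference shrinks; in the last cell EGD as practised is truly the less painful, so MACE should not win.

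*(c) The null that belongs to the planned contrast.* Set the MACE mean equal to the mean of the mixed EGD group (d = s × k/25). The test rejects in about 5% of trials for s = 1, 4% for s = 2 and 3 to 4% for s = 3. It does not exceed its nominal level.

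**3. Mask adherence.** Suppose the mask is the only cause of a difference. Let b be the background count relative to unmasked emission, a the share adhering and f the filtration. The expected MACE/EGD ratio is (b + 1 − a × f) / (b + 1).

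| adherence | b = 0 | b = 1 |
|---|---|---|
| 100% | 0.10–0.13 | 0.55–0.57 |
| 80% | 0.28–0.30 | 0.64–0.65 |
| 50% | 0.55–0.57 | about 0.78 |

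The same ratio, 0.55–0.57, fits full adherence with background or half adherence without it, so the ratio does not reveal adherence. In every row, though, the ratio is the contrast that the advised procedure produced.

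Poor adherence would cost power. With 25 per group and an assumed SD equal to the control mean, power is 87-89% at full adherence and 34-36% at half. Recording adherence would not restore it.

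**4. What splitting the EGD group would yield.** The 95% half-width for a mean difference is t(0.975) × √(1/25 + 1/n) in SD units: 0.57 for n = 25, 0.71 for n = 12 and 0.93 for n = 6. Sedation is chosen by the patient, so these estimates would be both imprecise and confounded.

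**5. How complete is Section XI?** Examination completion is a named secondary endpoint and does not appear there. Absence from that list is therefore weak evidence that an item will not be collected.

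**The case for a change.** The strongest case for acting is that a comparison of practices still needs a description of what each practice delivered. Readers elsewhere cannot apply the pain and willingness results without the share sedated, and the plan leans on mask wearing that it neither requires nor names for recording. Medication history sits with baseline information and does not plainly cover a drug given at the procedure. Acceptance of the examination does not plainly cover a mask. A few form fields would cost almost nothing, and mask behaviour may be lost if nobody notes it on the day.

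Much of this stands. The items are not named, and counts of patients sedated, masked and keeping their lips closed belong in any good report, preferably as separate items because Section XII relies on the mask alone. But this argues for ordinary completeness in the forms and the report. It does not show that a planned test, comparison or sample size would change. Recording adherence would not separate mask from device either, since mask use nearly coincides with group.

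**Conclusion.** No change to the plan is needed. The omission from Section XI is real, but it is missing detail that the case report forms may already cover and that analysts would ordinarily fill by reporting the counts in each group. MACE against all EGD is a legitimate contrast of two ways of examining the patient, and the test of it keeps its level: about 3 to 5% rejection under its own null in the cases tried. The large figures, up to 86% rejection or a fall from 79% to 1%, reflect real differences between the practices under assumed inputs. They bear on interpretation and on carrying the secondary results to centres with other sedation habits.

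The primary result should be read as MACE with mask and lip closure advised, against EGD as routinely performed; the abstract and background already tie the expected benefit to those measures.

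This rests on reading the objective as a comparison of practices, and on assumed values for pain SD, sedation effect, sedated share, particle variability and background level, none of which the documents give. If the sponsor wished to claim that the capsule itself emits less, or hurts less than unsedated EGD, the planned contrast would not support that, with or without the extra fields. How patients come into the two groups is a separate question.

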## IX. Required Medications or Medical Equipment and Quantities

- (I.) Magnetically Assisted Capsule Endoscopy (InsightEyes EGD): 50 sets
- (II.) Aries E500i Image Processor (including power cable) / Aries E500i (Model: FG-270-0008, Quantity: 1)
- (III.) InsightEyes Image Connector / InsightEyes EGD Dongle (Model: DG-001T, Quantity: 1): A connector that links the InsightEyes EGD to the image processor.
- (IV.) InsightEyes MFN Magnetic Controller / InsightEyes MFN (Model: FG-270-0001, Quantity: 1): A magnetic device used to manipulate and adjust the positioning angle of the InsightEyes EGD.

Stationary equipment: ② Aries E500i Image Processor ① Medical-grade monitor (not included in this product) ③ InsightEyes Image Connector  
 Controller: ⑤ InsightEyes MFN Magnetic Controller  
 Single-use medical devices: ④ InsightEyes EGD

The above equipment has been approved by the Taiwan Food and Drug Administration (TFDA) under Medical Device Permit No. 006509.

(V.) MET ONE airborne particle counter [DR-528 Handheld Particle Counter (Met One Instruments, Inc., Grants Pass, OR)]

**X. Format of medical record forms:** Study personnel will use separate case report forms (CRFs).

**XI. Methods for Data Collection, Processing, Evaluation, and Statistical Analysis**

**Approval Number: 202210059DIPA**

(I.) Collect and record the enrolled patients' basic information (including sex, age, height, weight, past medical history, and medication history), vital signs, pain index, blood test results within the past three months, and transient elastography values.

(II.) Document the examination results of both the Magnetically Assisted Capsule Endoscopy (MACE) and conventional esophagogastroduodenoscopy (EGD), including the presence of esophageal varices and bleeding sites.

(III.) Record the patients' acceptance of the examination and any adverse effects.

(IV.) Record the particle count measurements obtained using the MET ONE Airborne Particle Counter [DR-528 Handheld Particle Counter (Met One Instruments, Inc., Grants Pass, OR)].

## **XII.Statistical Analysis and Sample Size Calculation**

We will analyze the results using STATA (version 17) and MedCalc (version 20) statistical software. Continuous variables will be analyzed using the Student t-test or Mann-Whitney U test to assess differences between the "study group" and the "control group." Categorical variables will be analyzed using the Chi-square or Fisher's exact test. A p-value of <0.05 will be considered the threshold for statistical significance. For the sample size calculation, we assume that the study group will wear surgical masks for the examination, which have an approximate filtration efficiency of 87-90%. Based on a 95% confidence interval and a 5% margin of error, we estimate that enrolling 50 subjects (25 in the study group and 25 in the control group) will provide sufficient power to detect statistically significant results.

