## V. English Abstract

**Background and aims:** Biliary atresia (BA) is the leading cause of chronic liver insufficiency, liver cirrhosis, esophageal varices, and liver transplantation in the world. Regular endoscope examination with prompt adjustment of therapeutic agents is key to avoid the occurrence of esophageal varices bleeding. During the pandemic of COVID-19, to offer a regular and safe endoscopy survey of esophageal varices in BA patients become a medical challenge issue in the world.

Our study aim to investigate the diagnostic utility and safety of a Magnetically Assisted Capsule Endoscopy (MACE) system as comparing with traditional esophagogastroduodenoscope (EGD) in BA patients for the esophageal varices survey. We also aim to clarify whether the MACE is a less aerosol -generating procedure than EGD during the survey of esophageal varices, and decrease the risk of SARS-CoV 2 transmission.

**Methods:** This is an open-labeled un-blind trial. We intend to include 25 BA patients > 6 years of age agree to receive MACE examination into the study group, and another 25 BA patients > 6 years of age

Approval Number: 202210059DIPA

who will receive regular EGD into the control group. After the signature of the informed consent, they will enter this study. During the examination, a DR-528 Handheld Particle Counter (Met One Instruments, Inc., Grants Pass, OR) will be applied to detect aerosol generated during the examination. The compliance, diagnostic accuracy, and safety between study and control groups will be analyzed.

**Scientific merits and anticipated results:** The MACE was approved to achieve similar diagnostic accuracy and safety as EGD in adult population in Taiwan. Since subjects receiving MACE examination may close their mouth and have a face mask during the procedure, we intend to prove the MACE is an efficient, safe and less aerosol-generating procedure than EGD in BA patients this study. With the results of this study, we may offer the evidence of a safe and efficient examination during the pandemic of COVID-19 to protect the patients and medical staffs.

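### The inputs given for N = 50 do not produce 50, and they do not support the claim of sufficient power for the particle-count endpoint

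*Combined protocol and SAP*

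**What the plan says.** Section XII holds the only sample-size rationale. It has three inputs:

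- Masks: "we assume that the study group will wear surgical masks for the examination", "which have an approximate filtration efficiency of 87-90"%.
- Confidence level and margin: "Based on a 95% confidence interval and a 5% margin of error, we estimate that enrolling 50 subjects", split 25 and 25.
- Significance threshold: p < 0.05, sidedness not stated.

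From these it concludes that the enrolment "will provide sufficient power to detect statistically significant results". It names no formula and gives no numerical power. It also gives no target difference in counts, SD, coefficient of variation (CV) or control-group mean.

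The primary endpoint, in Section VIII (II) B (B), is the "difference in the number of droplet particles generated during the examinations between the" two groups. The analysis in Section XII is "Continuous variables will be analyzed using the Student t-test or Mann-Whitney U test".

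Two other places bear on the mask assumption. The abstract (Section V) gives two reasons for expecting fewer aerosols: "Since subjects receiving MACE examination may close their mouth and have a face mask during the procedure". Section VIII (II) B (A) makes masking a matter of advice: "Patients undergoing MACE will be advised to keep their lips closed and wear a surgical mask during the examination".

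**The concern.** A confidence level with a margin of error describes how precisely one quantity is estimated. It does not give the power of a two-group comparison. Section XII moves from one to the other without a step between them, and does not say what the 5% margin is a margin of.

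The filtration figure does not close the gap. It is a property of mask material. Nothing in the plan shows that it equals the difference the counter will record between two different procedures, one with closed lips and an advised mask. Section XII labels mask wearing as an assumption, but not the carry-over of filtration to the measured count.

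This is the sole basis for N and the sole power statement for the primary endpoint. As written, a reader cannot tell which difference the trial was sized to detect, on which scale, or with which of the two tests. A non-significant result would then be hard to interpret.

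**Working it through.** **Reading 1: precision of one proportion.** This is the natural formula that uses all the stated inputs: p = 0.87 or 0.90, z = 1.96, margin E = 0.05.

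n = z² p(1−p) / E²

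- p = 0.87: 3.8415 × 0.1131 / 0.0025 = 173.8, so 174.
- p = 0.90: 3.8415 × 0.0900 / 0.0025 = 138.3, so 139.

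The stated 50 is not reproduced. Turned round, the margin is z √(p(1−p)/n):

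| n | p = 0.87 | p = 0.90 |
|---|---|---|
| 50 (all patients) | 9.3 points | 8.3 points |
| 25 (study group, assumed masked) | 13.2 points | 11.8 points |

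A 5-point margin at n = 50 needs p(1−p) = 50 × 0.0025 / 3.8415 = 0.0325, so p is about 0.966, outside 87-90%.

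Variants do not rescue the figure:

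- One-sided z gives 123 or 98.
- p = 0.5 gives 385.
- Taking 5% as the full width gives 696 or 554.
- Estimating a difference between two proportions in this range to ±5 points needs 277-348 per group.

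In the attempts made, 25 per group (or within one of it) or 50 in total appeared only with inputs the plan does not state: a finite population of about 70-78, a 50% comparator, or a standardised difference of 0.8.

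**Reading 2: 5% is alpha and 87-90% is the effect.** No sum is then wrong, but N for a comparison of means also needs an SD and a target power. The plan gives neither, so N cannot be derived.

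**What 25 + 25 delivers.** Noncentral t, 48 degrees of freedom, noncentrality d√(25/2), alpha 0.05 taken as two-sided:

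- 80% power at d = 0.81.
- 90% power at d = 0.94.
- 41% power at d = 0.5.

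For normal data only, dividing by √(3/π) = 0.977 gives Mann-Whitney equivalents of about 0.83 and 0.96.

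**Why 87-90% alone does not fix the power.** Every spread below is an assumption. The first three rows suppose that the full reduction r = 0.87-0.90 reaches the counter.

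| Model, 25 per group | Spread 1 | Spread 1.5 | Spread 2 |
|---|---|---|---|
| Equal CV, noncentral t, d = r / (CV √((1+(1−r)²)/2)) | about 99% | 80-83% | 56-59% |
| Common SD as a multiple of the control mean, d = r / multiple | 85-88% | 52-55% | 33-34% |
| Lognormal counts, equal CV, simulated t-test (Mann-Whitney about 100% throughout) | over 99% | about 98% | 91-93% |
| Lognormal, only a 50% reduction reaches the counter: t-test | about 70% | 41% | 27% |
| The same: Mann-Whitney | 79-80% | 56-58% | 44% |

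The common-SD row is the less plausible one. With the study-group mean at 10-13% of control, it implies a study-group SD about 8 to 20 times that group's own mean. Simulated values carry an error of up to about 2 points.

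**The case against.** The strongest reply is that the trial may be well powered anyway. If the full 87-90% reduction appears in the counts and they are roughly lognormal with a CV up to 2, power is at least 91% with the t-test and near 100% with Mann-Whitney. The lower full-reduction figures come from normal theory on non-negative counts; a normal distribution with CV 2 would put about 31% of values below zero. The 50% reduction is not in the plan. A closed mouth in addition to a mask could also make the reduction larger than filtration alone. All of this stands, and it is why the finding is not one of proven under-powering.

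It is also fair that Section XII names no formula, so 139-174 rests on a formula supplied here, and that on the alpha reading there is no miscalculation. But that reading yields no N at all. The favourable scenarios need a spread and a carry-over that the plan does not state, so they cannot be what its power claim rests on.

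A small investigator-initiated study may choose a practical N and say so. Section XII instead presents a calculation with a power conclusion.

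**Conclusion.** The concern holds. As a precision calculation the inputs give 139-174 and a margin of 8.3-9.3 points at n = 50. As a power calculation they lack an SD and a target power. The power claim for the particle-count comparison is therefore unsupported as written.

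This does not establish that 25 per group is inadequate. Depending on the spread and on the reduction that reaches the counter, it could be ample or insufficient. Nor should 139-174 be adopted as a target, since that range answers a question about one proportion that the trial does not ask. The detectable differences given above rest on two-sided 0.05 (the usual reading of the stated threshold) and 25 usable measurements per group.

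**What to change.** Replace the sample-size text in Section XII. Keep N = 50 and the planned tests, and delete the margin-of-error basis and the unqualified power claim. Suggested wording:

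> With 25 per group and two-sided alpha 0.05, a Student t-test has 80% power for a standardised difference of 0.81 and 90% for 0.94; power at 0.5 is 41%. For normally distributed data the Mann-Whitney equivalents are about 0.83 and 0.96; for skewed counts they differ.

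If the 87-90% reduction is kept, label its carry-over to the measured count as an assumption. State the scale, the test and an SD with its source, or say that no source exists. Without this second part the reader still will not know which difference in particle counts was intended. Do not insert a raw-count power range based on a common SD alone: omit it, or show it beside the equal-CV range with both labelled as assumptions.

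The cost is one paragraph, with no added patients and no change to the analysis. The stated justification becomes less favourable, and an SD source must be found or its absence admitted.
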